### **Objectives:**

In this study, we aim to evaluate the gait differences among three different walking modalities with respect to spatiotemporal gait parameters. This will be achieved through a comparative analysis of spatiotemporal data between those groups. To ensure the safety of the subjects, the data collection protocols will be strictly followed, incorporating already tested procedures that have shown no probable risk. The BWSS has been tested with healthy individuals and is manufactured using widely available components in Bangladesh. The objectives of the study are as follows:

- **Study objectives:** To evaluate the variations in spatiotemporal gait parameters of three different walking modalities and analyze and determine which walking technique provides the most reliable gait metrics, suggesting a more stable and possibly advantageous recovery outcome.
- **Study Hypothesis:** We hypothesize that body weight supported treadmill walking will exhibit the least variability in spatiotemporal gait parameters compared to overground walking and self-paced treadmill walking. This suggests that BWST provides a more controlled environment, promoting more consistent and reliable gait patterns, which may translate to a more stable and potentially advantageous recovery outcome for individuals with stroke.

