Understanding the variability of gait parameters across these environments is important for several reasons. Identifying the environment that produces the most consistent and reliable gait data enables researchers and clinicians to select the best assessment method for post-stroke patients. This can result in more accurate assessments of gait impairments and progress during rehabilitation. Therapists can tailor gait training programs to specific environments based on rehabilitation objectives and individual needs. For example, because of its supportive nature, BWST may be a useful tool for initial training, whereas overground walking practice becomes more critical as balance and coordination improve. Additionally, it will provide a reliable and safe method for gait analysis that can be widely adopted in Bangladeshi healthcare setting and lay the groundwork for future research and clinical applications in gait analysis and rehabilitation for stroke patients in Bangladesh. Ultimately, this study seeks to improve the assessment and management of gait impairments in stroke patients, contributing to better rehabilitation outcomes and enhancing the quality of life for affected individuals.

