## **Data collection procedure:**

Participants will be selected based on pre-determined inclusion criteria to ensure they fit for the study. Data will be collected through face-to-face interview using a pretested semi-structured questionnaire and informed verbal consent will be taken prior to interview. All the participants demographic information (age, weight, height, etc.) will be collected. Participants evaluated by Berg Balance test and Time Up & Go (TUG) test questionnaire form. All participant names have been properly defined to make sure confidentiality. After that the participants will be instructed to walk in their natural and comfortable manner. All participants will undergo a familiarization trial to get comfortable with the experimental setup and procedures. Then, participants will perform linear walking during two consecutive trials. Then take 2 minutes rest for treadmill walking after that again take 2 minutes rest for BWSTW. Data will be collected using a force plate and an 8-camera video monitoring system on all three walking modalities. The collected spatiotemporal data will be analyzed by statistical methods to identify differences among those modalities. Specific focus will be on key spatiotemporal parameters such as step length, stride length, cadence, gait speed, and the duration of the stance and swing phases use as important aspects of gait analysis

**Figure:** Flow chart of study plan

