**Table 1: Summary of the comparative study between healthy and post stroke individuals**

Aspect of the study	Description
Study Type	Comparative
Design	Comparative study
No of subjects	25
Objective	Evaluate the variations in spatiotemporal gait parameters of those
waking modalities.	
Study Population	Inclusion Criteria for post-stroke patients:

	
 
Participants must be between 18 to 75 years old.
 
More than 1- month post stroke.
 
Participants must be able to walk with or without assistance.
 
Patients including both the male and female.
 
Participants must be able to provide informed consent to participate in the study.
 
 
Exclusion Criteria for post-stroke patients:
 
 
Severe cognitive or communicative disorders.
 
Significant joint malposition.
 
Psychological, cognitive dysfunction, and any other neuromuscular problem.
 
Pregnant women will be excluded to avoid any potential risks to the mother and fetus.
 
Unstable cardiovascular disease
 

Procedure	
Post stroke group:
 
 
Giving instruction
 
Randomly assigning patients to all the modalities
 
Data collection through force plate and video cameras
 
Extracted spatiotemporal parameters from recorded data
 

Outcomes	
Primary Outcome:
 
 
Gait velocity
 
 
Secondary Outcome:
 
 
Step length
 
Stride length
 
Cadence
 
Stance and swing phases duration
 
Single and double support time
 
Ground reaction force
 

Data Collection	
Data collected before trial:
 
 
Patient clinical condition
 
Time after stroke and before data collection
 
Duration of therapy/rehabilitation
 
 
Data collected during walking:
 
 
Force plate data
 
Video monitoring data
 

Data analysis	
 
Comparative test between the primary outcome of three group
 
Wilcoxon sign rank test & a paired sample t test
 
Interclass correlation coefficient between those group
 
Mean difference and standard deviation between those group
 

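### The planned correlation coefficient between modalities measures their agreement, and no listed analysis measures the repeatability of each modality that the objective asks about

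*Protocol*

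**What the plan says.** **Aim.** Annexure C, Objectives, sets out to "determine which walking technique provides the most reliable gait metrics" and hypothesises that "body weight supported treadmill walking will exhibit the least variability in spatiotemporal gait parameters". The Rationale gives the intended use: "Identifying the environment that produces the most consistent and reliable gait data enables researchers and clinicians to select the best assessment method". Reliability is thus treated as low variability, a property of each modality that is to be compared across the three.

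**Analysis.** The Data analysis row of Table 1 has four entries:
- a comparative test of the primary outcome, gait velocity, over the three groups;
- a Wilcoxon signed-rank test and "a paired sample t test";
- "Interclass correlation coefficient between those group";
- "Mean difference and standard deviation between those group".

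**Repeats.** In the Data collection procedure, "participants will perform linear walking during two consecutive trials". For the treadmill modes it says only "Then take 2 minutes rest for treadmill walking after that again take 2 minutes rest for BWSTW", with no number of trials. The Case Report Form has one walking-speed entry and no field for modality or trial.

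**The concern.** A coefficient computed between modalities answers whether they give similar values for the same patient. The objective asks something else: how closely one modality reproduces its own values in the same patient, and for which modality that is closest. No entry in the row is stated as a within-person measure for each modality.

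Followed as written, the study would report agreement between modalities against an objective about the reliability of each. It could then not support a choice of assessment environment, which is the use that the Rationale gives for the result.

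**Working it through.** **Inputs.** The Protocol gives no figure for reliability. The only figure taken from it is the SD of 0.3 in the sample size section. That calculation reproduces: 2 × 0.3² × (0.8416 + 1.96)² / (0.17² × 2) = 24.44, against 24 stated. It has no bearing on this point. The Protocol does not say whether 0.3 is an SD across patients or of differences; here it is assumed to be across patients, so the between-person variance is B = 0.09. All trial SDs below are assumptions, and two trials per modality are assumed.

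**Step 1: within each modality.** ICC = B / (B + trial variance). For trial SDs of 0.20, 0.10 and 0.05:
- 0.09 / (0.09 + 0.04) = 0.69
- 0.09 / (0.09 + 0.01) = 0.90
- 0.09 / (0.09 + 0.0025) = 0.97

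**Step 2: one coefficient over the three modalities.** With two-trial means the error variances are 0.02, 0.005 and 0.00125, with mean 0.02625 / 3 = 0.00875. ICC = 0.09 / (0.09 + 0.00875) = 0.911. Only the mean error variance enters, so exchanging the modalities changes nothing.

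A second assumed set, single trials with SDs of 0.05, 0.15 and 0.25, gives 0.09 / (0.09 + 0.0875 / 3) = 0.755. A simulation of 200,000 persons gave 0.75 to 0.76 in all six orderings, while the within-modality values were about 0.97, 0.80 and 0.59.

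**Step 3: pairwise coefficients, one common true value per person.** ICC = B / (B + mean error variance of the pair). With the error variances of step 2:
- modalities 1 and 2: 0.09 / (0.09 + 0.0125) = 0.878
- modalities 1 and 3: 0.09 / (0.09 + 0.010625) = 0.894
- modalities 2 and 3: 0.09 / (0.09 + 0.003125) = 0.966

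These differ. The three sums of error variances that they imply can be solved for the three separate variances, so under this model the ranking is recoverable.

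**Step 4: pairwise coefficients when patients respond differently to body-weight support.** Assume single trials with SD 0.20 overground and on the self-paced treadmill, and 0.05 with body-weight support. Add a patient-specific effect under body-weight support.

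| Assumed SD of patient-specific effect | Pair without body-weight support | Each pair with body-weight support | Within body-weight support |
|---|---|---|---|
| 0.20 | 0.09 / 0.13 = 0.692 | 0.09 / (0.09 + (0.04 + 0.0425) / 2) = 0.686 | 0.13 / 0.1325 = 0.98 |
| 0.25 | 0.09 / 0.13 = 0.692 | 0.09 / (0.09 + (0.04 + 0.065) / 2) = 0.63 | 0.1525 / 0.155 = 0.98 |

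The other two modalities have a within-modality ICC of 0.69. In the first row the pairs hardly differ. In the second, the most repeatable modality looks worst.

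**Step 5: an SD per modality across patients.** When the trial SD falls fourfold, from 0.20 to 0.05, the total SD moves only from √(0.09 + 0.04) = 0.36 to √(0.09 + 0.0025) = 0.30.

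**The case against.** - **Pairwise coefficients do carry a ranking.** This stands for the model of step 3. A reader might infer that no between-modality coefficient can ever name the most reliable modality. That is too strong: it is true of the single three-way coefficient, but for pairs it depends on a common true value per person. The Protocol does not state that assumption, and step 4 shows what happens when it fails.
- **The plan already lists a variability statistic, the SD.** A reader might infer that variability is left out altogether, and the last entry of the row shows otherwise. But that entry is worded as between groups. Even read as one SD per modality, it is dominated by differences between patients (step 5).
- **The wording is loose.** Interclass may be a slip for intraclass, and the reference to groups could mean a coefficient for each modality, then compared. This is possible, since the SD entry uses the same phrase and could be read in that way. The direct reading is still a coefficient between modalities, and correcting the slip alone would not change that.
- **Agreement is a legitimate question in a comparative study.** Agreed. The Objective row of Table 1 speaks only of evaluating variations and does not tie the coefficient to reliability. The coefficient can stay, under the right name.
- **Details of the coefficient may be left to an analysis plan.** Its form and model may be. The comparison it addresses is fixed here.
- **The treadmill modes lack repeats.** A reader might infer this, but the Protocol only leaves the number of treadmill trials unstated, and recordings can be divided into blocks.

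**Conclusion.** The point holds as a mismatch between the objective and the listed analyses. The row gives agreement between modalities, comparisons of location and a between-group spread. It names no within-person repeatability for each modality, which is what the objective and hypothesis need.

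That the three-way coefficient is blind to which modality is best follows from its symmetry, whatever the SDs. The sizes shown (0.911 or about 0.755 between modalities, against 0.69 to 0.97 or 0.59 to 0.97 within) rest on the assumed trial SDs and on reading 0.3 as a between-person SD. The failure of the pairwise ranking rests on an assumed patient-specific effect of body-weight support.

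A reader might infer that the primary comparison of gait velocity is also undermined. Nothing here supports that: it is a comparison of location and does not use this coefficient.

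**What to change.** Replace the correlation entry in the Data analysis row of Table 1 with wording such as:

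*Reliability: within-person SD (standard error of measurement) or coefficient of variation across trials or stride blocks within each modality, compared across the three modalities within patients, with 95% confidence intervals. Supplementary: intraclass correlation for repeated trials or blocks within each modality. Any intraclass correlation between modalities is reported as agreement.*

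The within-person SD or CV should lead because the ICC also depends on the spread between patients. With the same trial SD of 0.20, the ICC is 0.69 when the between-person variance is 0.09, and 0.1525 / 0.1925 = 0.79 when a patient-specific SD of 0.25 is added, although repeatability is unchanged.

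Use the two overground trials, and split each treadmill recording into two blocks. Store the value for each modality and for each trial or block, for which the Case Report Form has no field at present.

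The cost is one line in Table 1 and a little more analysis, with no extra walking or visit. Estimates will be less precise where few strides are recorded. Two separate overground trials also include the variation from starting again, which two blocks of one continuous walk do not. The report should say so and, where strides suffice, add the stride-to-stride SD for all three modalities.

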### **Introduction:**

Stroke is the leading cause of disability worldwide, affecting the lives of millions of people. One of the most debilitating effects of stroke is impaired gait, which impairs mobility and independence [1]. It is especially prevalent in low- and middle-income countries such as Bangladesh. Stroke is the third leading cause of death from non-communicable diseases in Bangladesh, putting a significant burden on both individuals and the healthcare system. Stroke prevalence in Bangladesh is around 11.39 per thousand people, with higher rates in rural areas and among elderly males [2]. Gait abnormalities are experienced by about 80% of stroke survivors, and they can significantly impair their daily activities and overall quality of life [3]. The significant number of disability-adjusted life years (485 per 10,000 people) lost due to stroke severely impacts the nation's economy [4]. Despite the high occurrence of disability due to stroke in Bangladesh, there are significant limitations in analyzing the gait characteristics of stroke patients. Gait rehabilitation uses a variety of walking modalities, such as body weight supported treadmill walking, self-paced treadmill walking, and overground walking. Every modality has particular benefits and drawbacks. The most natural kind of gait training is provided by walking on terrain that closely resembles actual walking conditions. However, because of the unpredictable nature of the environment and the lack of

mechanical support, it can be challenging for stroke patients [5]. Self-paced treadmill walking provides a controlled environment in which the patient's speed can be adjusted based on their abilities, allowing for a consistent walking rhythm and feedback [6]. This modality is useful for strengthening gait patterns and increasing endurance. However, body weight supported treadmill walking allows the patient to partially offload their weight, which lessens the pressure on their lower extremities and improves safety by lowering the chance of falls [7]. Variability in gait parameters such as step length, stride length, cadence, gait speed, and the duration of the stance and swing phases is an important aspect of gait analysis. High variability in gait frequently indicates instability and inefficiency, which are undesirable outcomes in rehabilitation. Lower variability, on the other hand, indicates more consistent and stable gait patterns, implying improved motor control and coordination.

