### Phase-3-Extended Study (0):

The aim of this phase of study is to compare the Spatiotemporal parameter among different waking modalities. The standard protocols will be followed while conducting experiment, in the Department of Biomedical Engineering (BME), BUET. The various aspect of this final and most important component of the study are described below:

**Sample Size calculation:** In this comparative study, the gait velocity in between different waking modalities is considered as the primary parameters. The following formula may use for calculating the sample size for each group of the trial:

$$\text{Sample size, } N = \frac{2\sigma^2(Z_{1-\beta} + Z_{1-\alpha/2})^2}{d^2(k-1)} \quad \dots \dots \dots \quad (i)$$

Where,

N = Required sample size

$d$  = Difference in means of two group (effect size)

$$\sigma = \text{SD}$$

**k** = is the number of groups being compared.

$Z_{1-\beta}$  = It is the desired power

$Z_{1-\alpha/2}$  = Critical value and a standard value for the corresponding level of confidence. (At 95% CI it is 1.96)

To estimate the sample size, we considered the mean difference of the velocity of the post stroke patient to be at least 0.17 with a standard deviation of 0.3. We estimated that 24 individuals would be needed to satisfy the comparative studies between three groups, based on the statistical power of 80%, at a two-sided alpha level of 0.05. The statistical formula (i) used for the comparative test [10]. Considering dropouts and left-against-medical advice (LAMA) cases, sample size  $N = 25$  will be considered. Thus, a total of 25 subjects will be considered for the equal allocation of this study. The different aspects of the study are summarized in Table I.

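### The hypothesis is about consistency of gait, but no listed analysis measures within-patient variability, and the one standard deviation listed cannot stand in for it

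*Protocol*

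**What the plan says.** The Objectives section of the protocol (Annexure C) hypothesises that "body weight supported treadmill walking will exhibit the least variability in spatiotemporal gait parameters". The Introduction gives the meaning: "Lower variability, on the other hand, indicates more consistent and stable gait patterns, implying improved motor control and coordination". The Summary likewise makes consistency of gait the basis for choosing between modalities.

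Table 1 names "Gait velocity" as the primary outcome. The secondary outcomes are step and stride length, cadence, phase durations, support times and ground reaction force. All of these are levels.

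The Data analysis row of Table 1 contains:
- "Comparative test between the primary outcome of three group";
- a Wilcoxon signed rank test and "a paired sample t test";
- "Interclass correlation coefficient between those group";
- "Mean difference and standard deviation between those group".

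The Case Report Form has one field each for walking speed and cadence, and one per leg for stride and step length. It has no field for an SD, a CV or per-stride values.

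**The concern.** Consistency that reflects motor control belongs to one person's successive strides, so the hypothesis needs a measure of spread within each patient in each modality. Nothing in the outcomes or the analysis row supplies one. The only listed quantity that resembles variability is a standard deviation whose unit is not stated, and neither natural reading of it is a within-patient spread.

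The stated hypothesis therefore has no analysis that could support or refute it. The Rationale wants the result to guide which environment is used for assessment and for training. A reader left with three across-patient SDs could take the smallest as evidence of the steadiest gait, when it may show only that patients resembled one another more in that modality.

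**Working it through.** **1. The plan's own figure.** Formula (i) under Sample Size calculation, with a difference of 0.17, an SD of 0.3, k = 3, 80% power and two-sided alpha 0.05:

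N = 2 × 0.3² × (0.8416 + 1.96)² / (0.17² × 2) = 24.44.

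The plan states 24 (25 after the dropout allowance), so its figure is reproduced apart from rounding down. It rests on a mean difference in velocity. Nothing in it concerns variability.

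**2. What each listed analysis measures.**

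| Entry in Table 1 | What it addresses |
|---|---|
| Comparative test on the primary outcome | Level of velocity |
| Wilcoxon signed rank and paired t tests | Difference in level between two modalities |
| Correlation coefficient | Agreement or association between modalities |
| SD, read as the spread of patient values in a modality | Mainly differences between patients |
| SD, read as the spread of paired differences | How unevenly patients change between two modalities |

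None is a within-patient, stride-to-stride quantity.

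**3. First reading: SD across patients in a modality.** If each patient's value is the mean of m strides,

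SD_across = √(SD_between² + SD_within²/m).

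Assumptions: SD_between = 0.3 (the plan gives "with a standard deviation of 0.3" but does not say that it is a between-patient SD), m = 10, and stride SDs of 0.06 and 0.12. The documents give no stride SD or stride count.

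- Stride SD 0.06: √(0.09 + 0.0036/10) = 0.3006
- Stride SD 0.12: √(0.09 + 0.0144/10) = 0.3024
- Change: 0.3024/0.3006 − 1 = 0.6%
- Relative standard error of an SD at n = 25: 1/√(2 × 24) = 14.4%

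A twofold difference in stride consistency is far below what this SD can resolve. Over a wider range (SD_between 0.2 to 0.4, m = 5 to 50, stride SD 0.03 doubled to 0.06) the change is at most 0.7%.

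**4. What would happen if this SD were used to rank modalities.** This was simulated with 20,000 studies of 25 patients, stride SD 0.03 against 0.06, SD_between = 0.3, correlation between modalities 0.5 to 0.95, and 2, 10 or 20 strides per patient.

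| Setting | Steadier modality ranked first |
|---|---|
| By across-patient SD, equal SD_between | 50–54% |
| By across-patient SD, SD_between 10% larger in the steadier modality | 8–32% |
| By mean within-patient SD | more than 99% |

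**5. Second reading: SD of paired differences.** With correlation 0.8 and m = 10,

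√(2 × 0.3² × (1 − 0.8) + (0.03² + 0.06²)/10) = 0.191.

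Exchanging the two stride SDs leaves it at 0.191. It is one symmetrical number per pair and cannot say which modality is steadier.

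**The case against.** The strongest reply is that Table 1 sets the SD beside the mean difference, directly after the paired tests and the correlation coefficient. It may be no more than the summary that accompanies the paired comparison. No section says that the modality with the smallest SD will be declared the most consistent. That stands: a reader might infer such a rule, but the protocol does not contain it. The percentages in step 4 score that inferred rule and do not describe a planned analysis.

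A reader might also conclude that the ranking is a coin toss. That holds only if between-patient SDs are equal across modalities, and it rests on assumed stride SDs, stride counts and correlations. The 0.3 serves equally well as an SD of paired differences: (0.3 × 2.8016/0.17)² is again 24.44.

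The protocol also uses its terms loosely. The Objectives speak of gait differences and reliable metrics, and the Rationale of data variability from the environment. The correlation coefficient may be aimed at reliability. Even so, it measures agreement between modalities, and the Introduction ties variability to motor control.

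Finally, how an SD is computed can be left to an analysis plan. But this protocol already fixes a variability hypothesis alongside outcomes, analyses and a case report form that do not address it. That is a mismatch in what is stated, beyond missing detail.

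**Conclusion.** The concern holds in this form: the plan names no statistic capable of testing its own variability hypothesis, and the one dispersion statistic that it lists cannot serve under either reading. This follows from the definitions and needs no assumed numbers.

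The size is conditional. If across-patient SDs were used to judge consistency, the ranking would be near chance under equal between-patient SDs of 0.3 (a 0.6% signal against about 14% sampling error). It could be systematically wrong if patient heterogeneity differs by modality. The documents do not support saying that the plan has adopted this ranking.

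Nor does the point touch the comparison of mean gait velocity, which has its own tests and a sample size that can be reproduced.

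**What to change.** In the Data analysis row of Table 1, add as the analysis of the hypothesis in the Objectives:

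- For each patient, modality and parameter, compute the within-patient stride-to-stride SD and CV from the planned recordings.
- Compare modalities by the paired log ratio of this quantity, with a 95% confidence interval.
- Use the same number of strides per patient in each modality, and state that number.

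Define the SD in the existing entry. Keep the across-patient mean and SD as descriptive, and say that they are not used to judge consistency. Add per-stride values, or the within-patient SD, to the Case Report Form.

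The cost is more than wording, because strides must be extracted individually and the form must change. The weak point is overground walking: Data collection procedure gives two consecutive linear trials, and no stride count is stated for any modality. By the same formula, a per-patient SD has a relative standard error of about 1/√18 = 24% from 10 strides and 1/√6 = 41% from 4. Averaging over 25 patients helps, but if too few overground strides are usable, the variability conclusion should be limited to the modalities and parameters with enough strides.
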